3.4.2.3 Overview of Safety

An overview of data are provided below and described in detail in the rucaparib IB.

Integrated Safety Analysis in the Treatment Setting (Studies CO-338-010 and CO-338-017)

An integrated safety analysis, based on pooled safety data from 545 patients in Study CO-338-010 (Parts 2A and 2B) and Study CO-338-017 (ARIEL2; Parts 1 and 2) with relapsed ovarian cancer who were treated with 600 mg BID monotherapy rucaparib, was performed and a summary of TEAEs, overall and \geq Grade 3, is presented in [Table 1](#). This analysis includes data as of 1 September 2017. Overall, the median duration of treatment was 160.0 days (approximately 5.3 months; range, 2 to 1234 days).

The most common TEAEs reported were primarily mild to moderate (Grade 1-2) in severity and included gastrointestinal disorders (nausea [78.5%], vomiting [45.9%], constipation [37.6], abdominal pain (32.5%), and diarrhea [32.3%]), asthenia/fatigue (75.0%), anemia/decreased haemoglobin (44.0%), ALT/AST increased (39.3%), decreased appetite (38.3%), and dysgeusia (36.7%).

The most common treatment-related TEAEs reported were primarily mild to moderate (Grade 1-2) in severity and included nausea (68.3), asthenia/fatigue (67.0%), anemia/decreased haemoglobin (38.9%), ALT/AST increased (36.5%), dysgeusia (34.1%), and vomiting (31.6%) as described in greater detail in the rucaparib IB.

The most common TEAEs \geq Grade 3 were anemia/decreased hemoglobin (24.2%), asthenia/fatigue (11.7%), ALT/AST increased (10.8%), thrombocytopenia/decreased platelets (6.1%), and nausea (5.3%). As of the data cut-off date, approximately 9% of patients had discontinued due to a treatment-related TEAE.

In addition, photosensitivity has been reported in some patients. Photosensitivity was initially reported in the Phase 1 dose-escalation portion of Study CO-338-010 (n=6; 10.7%) and based on these reports of photosensitivity, guidance for sun protection was included in rucaparib clinical studies. Of 917 patients with advanced ovarian cancer treated with rucaparib 600 mg BID in Studies CO-338-014 (ARIEL3), CO-338-010, and CO-338-017 (ARIEL2), 118 patients (12.9%) experienced photosensitivity, of whom 2 patients (0.2%) experienced \geq Grade 3 photosensitivity as described in the rucaparib IB. Patients should use typical precautions when going outside, such as applying sunscreen (sun protection factor 50 or greater) and/or covering exposed skin with clothing and wearing a hat and sunglasses.

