Quantitative variables will typically be summarized using frequencies and percentages for appropriate categorizations and may also be summarized using descriptive statistics. For variables summarized with descriptive statistics, the following will be presented: N, mean, standard deviation, median, minimum, and maximum. Categorical variables will be presented using frequencies and percentages.

The Kaplan-Meier methodology will be used to summarize time-to-event endpoints. If estimable, the 50th percentile (median) with the 95% confidence interval and range (minimum, maximum) will be summarized. The number of patients with events and the number of censored patients will also be presented.

All data will be used to their maximum possible extent but without any imputations for missing data. Unless otherwise specified, baseline is defined as the last measurement on or prior to the first day of study drug administration.

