11 STATISTICAL / ANALYTICAL ISSUES

11.1 Handling of Dropouts or Missing Data

All data will be used to their maximum possible extent but without any imputations for missing data. All time to event analyses include censoring and the rules for deriving the censoring value are described in more detail under each one of the time to event endpoints.

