12 SAFETY ANALYSIS

The safety analyses will be performed using the safety population. In general, safety analyses will be presented by gene mutation (e.g., BRCA1/2, ATM, CDK12, CHEK2, and Other) and Overall. Safety data may also be presented by measurable disease status at baseline to explore the safety profile between patients with and without measurable disease at baseline. Additionally, safety data will be further explored by age group (< 65, 65-74, ≥ 75) and race (White, Other).

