12.1 Adverse Events

Adverse events will be classified using the Medical Dictionary for Regulatory Activities (MedDRA) classification system. The severity of the toxicities will be graded according to the NCI CTCAE version 4.03 or higher whenever possible. Treatment-emergent adverse events (TEAEs) are defined as AEs with onset date on or after the date of first dose of study medication until the date of the last study medication dose plus 28 days. Adverse events will be considered treatment-emergent if all or part of the date of onset of the adverse event is missing and it cannot be determined if the adverse event meets the definition for treatment-emergent.

The number and percentage of patients who experienced TEAEs for each system organ class and preferred term will be presented. Multiple instances of the TEAE in each system organ class and multiple occurrences of the same preferred term are counted only once per patient. The number and percentage of patients with at least one TEAE will also be summarized.

MedDRA preferred terms will also be combined and presented in summaries for the following similar terms:

- Asthenia/Fatigue;
- ALT/AST Increased;
- Anemia and/or Decreased Hemoglobin;
- Thrombocytopenia and/or Decreased Platelets; and
- Neutropenia and/or Decreased ANC.

Separate tables will be presented as follows:

- TEAE Overview;
- All TEAEs;
- Treatment-related TEAEs;
- Grade 3 or higher TEAEs;
- Grade 3 or higher treatment-related TEAEs;
- Serious TEAEs;
- Serious treatment-related TEAEs;
- TEAEs by CTCAE grade;

- Treatment-related TEAEs by CTCAE grade;
- TEAEs with an outcome of death;
- Treatment-related TEAEs with an outcome of death;
- TEAEs leading to discontinuation of study medication;
- Treatment-related TEAEs leading to discontinuation of study medication;
- TEAEs leading to reduction of study medication;
- Treatment-related TEAEs leading to reduction of study medication;
- TEAEs resulting in interruption of study medication;
- Treatment-related TEAEs resulting in interruption of study medication;
- TEAEs resulting in reduction or interruption of study medication;
- Treatment-related TEAEs resulting in reduction or interruption of study medication;
- TEAEs resulting in reduction or interruption or discontinuation of study medication; and
- Treatment-related TEAEs resulting in reduction or interruption or discontinuation of study medication.

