The incidence of TEAEs will be summarized by relationship to study drug according to the following categories: “treatment-related,” or “not treatment-related”. If a patient experiences multiple occurrences of the same AE with different relationship categories, the patient will be counted once, as a relationship category of treatment related.

If a patient experiences multiple occurrences of the same AE with different toxicity grades, the patient will be counted once for the maximum (most severe) toxicity grade. AEs with a missing toxicity grade will be presented in the summary table with a toxicity grade of “Missing.” For each toxicity grade, the number and percentage of patients with at least one TEAE of the given grade will be summarized.

Time to the first treatment-related TEAE that resulted in a dose reduction, interruption, or discontinuation of study drug is defined as 1+ the number of days from the first dose of study drug to the start of the first respective AE. The cumulative incidence will be presented in a Kaplan-Meier plot for just the patients with an event, and the median time to onset will be calculated along with the 95% CI. Additionally, the analysis of combined terms for anemia will be presented as a time to first event analysis, as described above.

Non-TEAEs (pre-treatment and post-treatment) will be presented in the by-patient data listings for the safety population.

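### SAP 12.1 plots adverse-event cumulative incidence in affected patients only, so every curve must end at 100% whatever the true risk

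*SAP*

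**What the plan says.** SAP section 12.1 defines a time from first dose to the first treatment-related TEAE that led to a dose reduction, interruption or discontinuation. On its presentation it says: "The cumulative incidence will be presented in a Kaplan-Meier plot for just the patients with an event". A median time to onset with a 95% CI is to be reported with the plot. The same treatment is extended to anemia: "Additionally, the analysis of combined terms for anemia will be presented as a time to first event analysis, as described above".

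Three general statements in the SAP bear on this:

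- Section 12: "The safety analyses will be performed using the safety population". Section 4 defines that population as everyone who received at least one dose.
- Section 11.1: "All time to event analyses include censoring", with the censoring rules to be found under each endpoint. Section 12.1 gives none for this analysis.
- Section 3, on Kaplan-Meier summaries: "The number of patients with events and the number of censored patients will also be presented".

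Section 12.1 also plans number-and-percentage tables on the full denominator, including one for "Treatment-related TEAEs resulting in reduction or interruption or discontinuation of study medication".

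**The concern.** Cumulative incidence at time t is the proportion of all treated patients who have had the event by t. If the plotted set contains only patients who had the event, that proportion is lost: the curve answers when affected patients were affected, not how many were affected by when. The label invites the second reading, and the median then looks like an onset time for the treated population.

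The tables give the final crude incidence but no time course. This plot is the only planned display of when these events start. As specified, it cannot show the risk by a given time, and it cannot compare that risk between gene groups, which is how section 12 says safety output will generally be shown. One report could show x% for an event in a table and 100% for the same event in a figure.

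The stakes are limited to a descriptive safety display. No endpoint, stopping rule or sample-size decision depends on it.

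**Working it through.** The plan gives no numerical result for this analysis, so there is no figure to reproduce.

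**1. The end value.** Let m patients all have the event. Nobody is censored, so the Kaplan-Meier product reduces to 1 − KM(t) = d(t)/m, where d(t) is the number of events by t. At the last event this equals 1 for any m. No assumption is involved.

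**2. Size with complete follow-up.** With N treated patients and p = m/N, the cumulative incidence function (CIF) is d(t)/N. The planned curve is therefore CIF(t)/p, too high by the factor 1/p.

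**3. With staggered data cut-off.** Each jump of the Aalen-Johansen curve has weight S(u−)/Y(u), where S is event-free survival and Y the number at risk. This weight does not decrease over time. The event-only curve gives all jumps equal weight and is scaled to end at 1. It is therefore never below the all-treated curve, and its median is never later.

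**4. Illustrative inputs (assumptions).** Protocol section 3.4.2.3 gives pooled ovarian data: anemia 44.0% (240/545), treatment-related anemia 38.9%, and median treatment duration 160.0 days. Whether these transfer to mCRPC is unknown, so a range of 20% to 70% is shown. Hazards are taken as constant, and the 28-day tail after last dose is ignored.

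- End-of-treatment hazard: ln 2/160 = 0.00433 per day.
- Event hazard: p/(1−p) × 0.00433.
- At p = 0.44: 0.00340 + 0.00433 = 0.00774 in total, so the event-only median is ln 2/0.00774 = 89.6 days. The CIF on that day is 0.44 × 0.5 = 0.22.
- All-treated median at p = 0.70: total hazard 0.00433/0.30 = 0.01444. Solving 0.70 × (1 − exp(−0.01444t)) = 0.50 gives t = ln(3.5)/0.01444 = 86.8 days.

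| Assumed risk p | Factor 1/p | Event-only curve reaches 50% | Treated patients affected by then | All-treated curve reaches 50% |
|---|---|---|---|---|
| 20% | 5.00 | day 128 | 10% | never |
| 38.9% | 2.57 | day 98 | 19% | never |
| 44.0% | 2.27 | day 90 | 22% | never |
| 70% | 1.43 | day 48 | 35% | day 87 |

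**5. Simulation check.** One data set of 360 patients was drawn at each of five risk levels under the same assumptions. Events numbered 19, 32, 67, 160 and 248 (crude 5.3%, 8.9%, 18.6%, 44.4% and 68.9%). The event-only curve ended at 100% in all five; the Aalen-Johansen curve ended at the crude proportion in all five. In the last data set it reached 50% at day 101 rather than day 87, which is sampling variation in a single draw.

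**6. Group comparison.** Keep the event hazard at 0.00340 but halve the median treatment duration to 80 days (hazard ln 2/80 = 0.00866). The total is 0.01207, so the event-only median moves from day 90 to ln 2/0.01207 = day 57, while the actual risk falls from 44% to 0.00340/0.01207 = 28%. The group with fewer affected patients gets the higher curve.

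**7. Against the SAP's own rules.** Restricting to affected patients is not an analysis of the safety population (section 12), and it leaves nothing to censor (section 11.1). Section 12.1 explains neither departure. The tension with section 3 is weaker, since reporting zero censored would satisfy it literally.

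**The case against.** The best defence is that the restriction is disclosed in the same sentence, that median onset among affected patients is a legitimate summary, and that a specific rule may qualify a general one. Readers also have the full-denominator tables, which cover this very composite, so 1/p is an overstatement only for someone who ignores both. On this view one noun phrase is wrong and a relabel cures it.

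Much of that is fair. The median is valid as a description of affected patients, the crude risk is recoverable, and a relabel is an acceptable minimum repair. Three smaller points also stand:

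- Section 12.1 does not itself say that this plot is split by gene group; that comes from the general statement in section 12.
- It is a reading, though the natural one, that the cross-reference for anemia carries the restriction to affected patients as well as the time definition.
- The SAP counts AEs with undeterminable onset dates as treatment-emergent but imputes nothing, so some events in the tables may have no plottable time.

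Disclosure does not turn the curve into a cumulative incidence, however, and the tables do not supply a time course. The optional mean-change plots for selected laboratory parameters (SAP 12.2) do not show event onset either.

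It can also be argued that an event starting after the last dose cannot change dosing, so that patients should leave the risk set at last dose. But an event beginning during an interruption can still lead to discontinuation, and last dose plus 28 days is the SAP's own TEAE window.

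**Conclusion.** The concern holds. Followed as written, section 12.1 produces a figure that is wrong for its label: it ends at 100% by construction, in conflict with SAP sections 12 and 11.1. That conclusion is algebraic and needs no assumption.

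The size depends on the event rate. For anemia at the ovarian rates, the end value is 2.3 to 2.6 times the observed proportion; over assumed rates of 20% to 70% the factor runs from 5.0 to 1.4. The day counts rest further on constant hazards and the ovarian treatment duration. The documents give no rate for the composite dose-modification event, so no factor can be given for it.

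This should be corrected before the analysis is run, but it does not touch the trial's efficacy conclusions.

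**What to change.** Replace the rule in SAP 12.1 as follows:

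- Use the whole Safety Population and plot the Aalen-Johansen cumulative incidence, with values and 95% CIs at fixed times, for example 3, 6 and 12 months.
- Treat death, and reaching the end of the TEAE window (last dose plus 28 days) without the event, as competing events. Censor only patients still inside that window at data cut-off.
- With complete follow-up the plateau then equals the n (%) in the tables. Count TEAEs with undeterminable onset dates separately when reconciling the two.
- Do not substitute an all-patient 1 − KM that censors at end of treatment: in the simulated data set with 44.4% affected, it ended at 92.7%.
- If onset among affected patients is also wanted, report its median and range, labelled *among patients with the event*, beside n/N, and do not call it cumulative incidence. This relabelling alone is the minimum repair, but it leaves the time course of risk unreported.
- State explicitly that the same method applies to the combined anemia terms.

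The cost is SAP wording and a small amount of programming. No new data are needed.

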12.2 Clinical Laboratory Evaluations

Clinical laboratory evaluations include the continuous variables for hematology, serum chemistry, and urinalysis. The laboratory values will generally be presented in SI units. The on-treatment period will be defined as the time from first dose to 28 days after the last dose of study drug. Laboratory values collected during the on-treatment period will be included in the summary tables. The laboratory values collected after the on-treatment period will only be presented in the data listings.

The summary of laboratory data will include tables based on CTCAE grades generally using CTCAE version 5.0. A few assessments (e.g., hyperglycemia, hypophosphatemia, and hyponatremia) may use version 4.03 as quantitative grading is not available in version 5.0. Where available, Baseline, Worst Post-baseline, and Shift to Worst Post-baseline grade during the on-treatment period will be summarized. The baseline value will be defined as the value closest to, but not subsequent to, the date of first dose.

The summary of laboratory data will also include descriptive statistics (N, mean, SD, minimum, median, and maximum) of the maximum, minimum, and last value during the on-treatment period. Summaries using descriptive statistics of the change from baseline to the maximum, minimum, and last value during the on-treatment period will also be given. Longitudinal plots of the mean (and/or percent) changes from baseline to each scheduled visit may also be presented for select laboratory parameters. These plots may exclude visits for which only a small percentage (e.g., $\leq 30\%$) of patients have data.

Supporting laboratory data including normal ranges and abnormal laboratory flags may be provided using by-patient listings. Separate listings may be produced for laboratory abnormalities that meet Grade 3 or 4 criteria according to CTCAE.

12.3 Vital Signs

The on-treatment period will be defined as the time from first dose to 28 days after the last dose of study drug. Vital sign measurements collected during the on-treatment period will be included in the summary tables. The vital sign measurements collected after the on-treatment period will only be presented in the data listings.

The summary of vital sign data will include descriptive statistics (N, mean, SD, minimum, median, and maximum) of the maximum, minimum, and last value during the on-treatment period. Summaries using descriptive statistics of the change from baseline to the maximum, minimum, and last value during the on-treatment period will also be given. The data will be presented separately for each sub-cohort and overall.

12.4 ECGs

ECGs are collected at Screening (within 28 days prior to enrollment), at the Treatment Discontinuation Visit, and if clinically indicated, at other times during the study. The following are measured or calculated: heart rate, PR, QRS, QT, and QTc. Descriptive statistics (N, mean, SD, minimum, median, and maximum) will be used to summarize ECG parameters at Screening and at Treatment Discontinuation.

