3.4.2.1 Overview of Pharmacokinetics and Drug-Drug Interactions

An overview of data are provided below and described in detail in the rucaparib IB.

Assessment of rucaparib PK in cancer patients showed an approximate dose proportional exposure after QD or BID dosing, rapid absorption with C_{max} achieved within 1.5 to 6 hours, and distribution into tissue. The oral bioavailability was 36% and elimination ranged from 11 to 29.8 hours. Rucaparib was moderately bound to human plasma proteins *in vitro*.

At a dose of 600 mg BID rucaparib, steady state was achieved after approximately 1 week. The absolute oral bioavailability was 37.2%. In the presence of a high-fat meal, there was a slight delay in absorption, but an overall increase in exposure and oral bioavailability (51.7% [fed] vs. 36.2% [fasted]).

In vitro, CYP enzymes were shown to contribute to rucaparib metabolism. In a preliminary assessment of rucaparib metabolism in patients, rucaparib biotransformation pathways included hydroxylation or oxidation, N-demethylation, deamination, and phase II methylation. A carboxylic acid metabolite (M324) and a phase II N-methylated metabolite of M324 (M338) were identified as major metabolites.

POPULATION PK ANALYSES

Drug interactions with rucaparib as a substrate were assessed in a population PK analysis. CYP2D6 phenotypes (poor metabolizers, intermediate metabolizers, normal metabolizers, and ultra-rapid metabolizers) and CYP1A2 phenotypes (normal metabolizers and hyperinducers) did

not significantly impact the steady-state exposure of rucaparib at 600 mg twice daily. Concomitant administration of strong CYP1A2 or CYP2D6 inhibitors did not significantly impact rucaparib PK. Current smokers had overlapping rucaparib exposures as compared to nonsmokers and former smokers. Collectively, the results suggest that CYP1A2 and CYP2D6 play limited role in rucaparib metabolism *in vivo*, and no rucaparib dose adjustment is needed when concomitantly administered with CYP1A2 or CYP2D6 inhibitors.

Concomitant treatment with PPIs did not show clinically significant effect on rucaparib PK. No dose modification is recommended based on use of PPIs.

EFFECT OF RUCAPARIB ON THE PHARMACOKINETICS OF OTHER DRUGS

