- If, after 42 days of interruption of rucaparib, the anemia has not recovered to CTCAE Grade ≤ 1 then the patient should be referred to a hematologist and analysis of the bone marrow with cytogenetic studies are recommended according to standard hematologic practice.

The bone marrow analysis should include a bone marrow aspirate (for cellular morphology, cytogenetic analysis, and flow cytometry) and a core biopsy (for bone marrow cellularity).

Management of Rucaparib Treatment-emergent ALT/AST Elevations:

- Grade 4 ALT/AST elevations: hold rucaparib until values have returned to Grade 2 or better, then resume rucaparib with a dose reduction. Monitor liver function tests weekly for 3 weeks after rucaparib has been restarted.
- Grade 3 ALT/AST elevations, in the absence of other signs of liver dysfunction, should be managed as follows:
 - Monitor liver function tests weekly until resolution to \leq Grade 2.
 - Continuation of rucaparib with elevation of ALT/AST up to Grade 3 is permitted provided bilirubin is $<$ ULN.
 - If patient has Grade 3 ALT/AST and continues on rucaparib, and levels do not decline within 2 weeks or they continue to rise, treatment interruption and resolution to \leq Grade 2 will be required before rucaparib can be resumed, either at the current dose or at a reduced dose.

For patients who meet treatment interruption guidelines above, treatment with rucaparib should be held until the toxicity resolves to \leq CTCAE Grade 2. Twice daily dosing may then be resumed at either the same dose or a lower dose, per investigator discretion. If treatment is resumed at the same dose, and the patient experiences the same toxicity, treatment should be interrupted, then resumed at a reduced dose following resolution of the event to \leq CTCAE Grade 2. If the patient continues to experience toxicity, additional dose reduction steps are permitted; however, the investigator should consult with the sponsor's medical monitor before reducing to 300 mg BID. If a patient continues to experience toxicity despite dose reduction

steps to 300 mg BID, or if dosing with rucaparib is interrupted for > 14 consecutive days due to toxicity, treatment should be discontinued, unless otherwise agreed between the investigator and the sponsor.

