9.10.3 Vital Signs

Vital signs will include blood pressure, pulse, and body temperature and will be taken after the patient has been resting for at least 5 minutes during screening, at study visits during the Treatment Phase, at the Treatment Discontinuation Visit and the 28-Day Follow-up Visit.

9.10.4 12-Lead Electrocardiogram

For all patients, 12-lead ECGs will be performed at the following times:

- Screening (within 28 days prior to enrollment)
- Treatment Discontinuation Visit

The following will be measured or calculated: heart rate, PR, QRS, QT, QTc, and rhythm. The investigator or qualified designee will review the ECGs locally and assess the results as normal or abnormal (clinically significant or not clinically significant).

If it is clinically indicated, ECGs can be performed at other times during the study.

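### SAP 12.4 reports ECGs as two unlinked visit summaries, omitting within-patient change, clinically indicated tracings and the investigator's assessment, so an ECG effect during treatment would be poorly characterised

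*SAP*

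**What the plan says.** SAP 12.4 gives the whole ECG method in one sentence: six descriptive statistics (count, mean, SD, median and the two extremes) "will be used to summarize ECG parameters at Screening and at Treatment Discontinuation". The parameters are heart rate, PR, QRS, QT and QTc. Rhythm, which Protocol 9.10.4 also records, is not in the list.

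The same section acknowledges that ECGs are collected at the two visits "and if clinically indicated, at other times during the study". Protocol 9.10.4 agrees: "If it is clinically indicated, ECGs can be performed at other times during the study". Protocol Table 5 schedules no ECG between Screening and Treatment Discontinuation. Protocol 9.10.4 also has the investigator or a qualified designee review each tracing and "assess the results as normal or abnormal (clinically significant or not clinically significant".

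For vital signs, SAP 12.3 goes further: "Summaries using descriptive statistics of the change from baseline to the maximum, minimum, and last value during the on-treatment period will also be given". SAP 12.2 plans the same for laboratory values and adds a shift to the worst post-baseline grade.

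**The concern.** Three kinds of ECG information are collected and reach no ECG summary: each patient's own change, the clinically indicated tracings, and the investigator's assessment. The SAP gives no reason for treating ECGs less fully than laboratory values and vital signs.

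At stake is how well the study report can describe ECG behaviour on rucaparib. Two separate tables do not show whether a long QTc at discontinuation is new or was already present at Screening. They say nothing about tracings taken in between. They also do not show how many patients moved from normal to clinically significant.

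**Working it through.** No sample size, margin or error rate is attached to the ECG analysis, so there is no planned figure to reproduce. The check is what the two visit tables can and cannot deliver.

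**1. Mean change.** Let f be the share of patients with a Treatment Discontinuation ECG. The Screening mean over all patients is f × (Screening mean of those with that ECG) + (1 − f) × (Screening mean of those without). Hence:

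difference between visit means = mean paired change + (1 − f) × (Screening mean of those with − Screening mean of those without).

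If f = 1, the second term vanishes and the two tables give the mean change. The documents state no f. For assumed values of 0.9, 0.7 and 0.5, the second term is 10%, 30% and 50% of the Screening gap between the two groups, and nothing in the planned output shows that gap.

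**2. Spread of change.** With equal SDs at both visits and within-patient correlation ρ, SD of change = SD × √(2(1 − ρ)). The documents give no ρ. Over an assumed range:

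- ρ = 0: 1.41 × SD
- ρ = 0.5: 1.00 × SD
- ρ = 0.7: 0.77 × SD
- ρ = 0.9: 0.45 × SD

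The same two tables fit all four, so the spread cannot be recovered even when f = 1.

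**3. Side by side with the rest of the SAP.**

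- Laboratory values (12.2): change from baseline to the highest, lowest and last value in the on-treatment period, plus grade shift to worst.
- Vital signs (12.3): the same three changes over the same period.
- ECGs (12.4): two visits; no change, no on-treatment period, no shift table, no listing.

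**4. Exposure at the one scheduled post-baseline ECG.** Protocol 9.6.1 gives no interval between last dose and the Treatment Discontinuation Visit. Protocol 3.4.2.1 says "elimination ranged from 11 to 29.8 hours". Reading that as half-life (an assumption), the fraction of drug left is 0.5^(hours since last dose / half-life). For assumed intervals:

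- 0 days: 100%
- 1 day: 22% to 57%
- 3 days: 1% to 19%
- 7 days: 0.003% to 2%
- 14 days: at most 0.04%

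The discontinuation summary can therefore mix tracings close to full exposure with tracings nearly free of drug, and no planned output separates them.

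**The case against.** The strongest reply is that little is lost. Protocol 9.6.1 gives every patient a Treatment Discontinuation Visit whatever the reason for stopping, and Protocol 5.3 closes the study once all have stopped. By the final analysis the two tables should hold largely the same patients, and their means would then nearly give the mean change. This stands in part. Patients who die, are lost, miss the ECG or move to the extension protocol still break the match, as does any earlier data cut. The spread of change stays unrecoverable regardless.

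Some stronger readings are tempting, and the documents do not support them:

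- **That only averages are reported, or that an on-drug effect could not be seen.** SAP 12.4 plans minimum and maximum, so an extreme QTc at discontinuation would show. Protocol 10.1 allows an adverse event to be concluded from an ECG, and SAP 12.1 would tabulate it. That route depends on the investigator recording the event: Protocol 10.5 sets recording criteria for laboratory values, and there is no such list for ECGs.
- **That the loss of precision is large.** The discontinuation patients are a subset of the screened ones, so the two means are correlated. Assume 300 treated, 70% with a discontinuation ECG, between-patient SD 20 ms and within-patient SD 12 ms. The variance of the difference in means is (400 + 144)(1/300 + 1/210) − 2 × 400/300 = 1.74, so the SE is 1.32 ms. The paired SE is √(2 × 144/210) = 1.17 ms. At an assumed 90% the pair is 1.08 and 1.03 ms; at 50% it is 1.67 and 1.39 ms. Precision is not the argument.
- **That the discontinuation ECG is drug-free.** Protocol 7.4.2 says "if dosing with rucaparib is interrupted for > 14 consecutive days due to toxicity, treatment should be discontinued", unless the investigator and sponsor agree otherwise. The 14-day figure above applies only to patients stopped after such a hold, and their number is not given. An ECG near the last dose is equally compatible with the text.
- **That QTc mixes different correction formulas across sites.** Neither ECG section names a formula, but nothing shows that sites used different ones.

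The stakes are also modest. Protocol 3.4.2.3 cites an earlier comprehensive ECG assessment showing low cardiac risk.

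**Conclusion.** The point holds as a gap in reporting. SAP 12.4 omits within-patient change, clinically indicated ECGs and the investigator's assessment from every ECG summary, and falls short of the SAP's own treatment of laboratory values and vital signs. An ECG effect during treatment would be poorly characterised.

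The omissions are read directly from the text and rest on no assumption. How far the difference in visit means departs from the mean paired change depends on how many patients lack a discontinuation ECG and how they differ at Screening, which the documents do not give. No efficacy conclusion is affected. The change is worth making because it is cheap, not because the trial is at risk.

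**What to change.** Add to SAP 12.4:

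1. For patients with both values, within-patient change from Screening to Treatment Discontinuation, and from Screening to the worst post-baseline value including unscheduled ECGs. State for each parameter which direction counts as worst, and label the worst-value rows as possibly symptom-triggered.
2. A shift table of the investigator's assessment (normal; abnormal, not clinically significant; abnormal, clinically significant) from Screening to worst post-baseline.
3. A listing of unscheduled ECGs with days since last dose.

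The cost is SAP wording and two or three outputs from data already collected. The drawback is that worst values favour patients who had extra tracings for symptoms, hence the label. The change does not supply a scheduled mid-treatment ECG; that limit lies in the protocol schedule and should be acknowledged when the ECG results are reported.
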